Hypothesis 2a: Following tango, a differential BOLD signal increase will be observed in the premotor area, supplementary motor area, and putamen during both imagined forward walking and imagined backward walking; following treadmill training, BOLD signal will increase in the primary somatosensory cortex and cerebellum during imagined forward walking, but not during imagined backward walking. No BOLD signal changes will occur in the stretching group.

Hypothesis 2b: *BOLD signal changes will be directly related to changes in actual locomotor performance.*

Hypothesis 3a: *Following tango, resting state functional connectivity of the premotor area, supplementary motor area, and putamen will increase; following treadmill training, resting state functional connectivity of the primary somatosensory cortex and cerebellum will increase. No changes will occur in the stretching group.*

Hypothesis 3b: *Changes in resting state functional connectivity of the locomotor control network will be directly related to changes in actual locomotor performance. No changes will occur in the stretching group.*

A3 Purpose of the Study Protocol

B Background

B1 Prior Literature and Studies

SIGNIFICANCE

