For **Aim 1**, we will employ a repeated measures ANOVA with group (tango, treadmill, and *stretching*) and time (pre-intervention, post-intervention, and *follow-up*) as factors to determine whether and how these interventions impact gait velocity, our primary variable for Aim 1. Similar analyses will also be performed for secondary variables of interest, including the MDS-UPDRS-III, mini-BESTest, and PDQ-39. *As a secondary analysis for gait velocity, MDS-UPDRS-III, and mini-BESTest, we will determine percent difference between OFF and ON medication values at pre-intervention and post-intervention time points and compare these difference values using RM ANOVAs with group and time as factors. (If prescribed medications change over the course of the study then levodopa equivalent daily dose will be included as a covariate in these analyses.) This will allow us to determine if response to medications was different before vs. after intervention and whether this effect differed between groups.* Analyses will be conducted using NCSS software (NCSS, LLC, Kaysville, UT). All imaging analyses will be conducted using Brain Voyager (Brain Innovation, Maastricht, The Netherlands) and custom written Matlab (MathWorks, Natick, MA) software. For **Aim 2**, we will apply random effects general linear model analysis using forward and backward imagined tasks as individual contrasts. A false discovery rate (FDR) correction will be used to compensate for multiple comparisons. BOLD signal changes within the previously specified regions of interest will be compared for pre- and post-intervention conditions. Additionally, the three groups will be compared to each other in the post-intervention condition using RFX ANCOVA. For **Aim 3**, we will use an independent component analysis (ICA) to examine the strength of the correlation coefficients for anatomical regions identified as part of the locomotor control network. The strength of these correlations before vs. after intervention will be compared via two-tailed RM ANOVAs with group and time as factors. Finally, we will correlate BOLD signal changes during the imagined walking tasks (Aim 2) and changes in connectivity (Aim 3) with changes in motor performance.

G4 Missing Outcome Data

For Aim 1 dropouts will be handled utilizing intent to treat analyses with the last observation carried forward. Dropouts will be excluded from analyses in Aims 2 and 3 as full imaging data are needed from two time points.

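### The correlations that test H2b and H3b name no imaging-motor pair and carry no stated multiplicity control, so the chance of a false direct relation is well above 5%

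*Combined protocol and SAP*

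**What the plan says.** Section A2 states H2b as "BOLD signal changes will be directly related to changes in actual locomotor performance" and H3b as "Changes in resting state functional connectivity of the locomotor control network will be directly related to changes in actual locomotor performance". Both predict a direction, and neither names a pair of measures.

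The only analysis offered for them is the last sentence of G3: "Finally, we will correlate BOLD signal changes during the imagined walking tasks (Aim 2) and changes in connectivity (Aim 3) with changes in motor performance". It does not say which region, task, connection or motor variable is meant, whether motor values are OFF or ON medication, whether arms are pooled, or what significance level applies.

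Other sections supply the candidates:

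- H2a names three regions for tango ("premotor area, supplementary motor area, and putamen during both imagined forward walking and imagined backward walking") and two more for treadmill training ("BOLD signal will increase in the primary somatosensory cortex and cerebellum during imagined forward walking"). H3a names the same five.
- G3 analyses BOLD signal "using forward and backward imagined tasks as individual contrasts".
- For connectivity, G3 will "examine the strength of the correlation coefficients for anatomical regions identified as part of the locomotor control network", without giving their number.
- C1 makes gait velocity the primary variable of Aim 1 and lists six further gait variables. G1 reports velocity both forward and backward.

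G3 does state one correction: "A false discovery rate (FDR) correction will be used to compensate for multiple comparisons". It stands in the Aim 2 model text, before the Aim 3 analysis and before the correlation sentence.

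**The concern.** H2b and H3b are worded as predictions to be confirmed, but the plan does not say which correlation, or how many, would confirm them. With several imaging changes and at least two candidate velocities, an analyst following G3 can run many correlations and report any that reach nominal significance. At 54 people, a correlation of 0.27 is enough.

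The link between brain change and walking change is what would join the imaging aims to the gait aim. If that link can arise by chance far more often than 5% of the time, a reported association says little about mechanism.

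**Working it through.** **The plan's own figures.** G1 gives no power, significance level or test count for these correlations. The nearest figures are the between-group powers for Aims 2 and 3, with 18 per group and three groups. They were checked with a one-way ANOVA and noncentral F, noncentrality N × f².

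- Aim 3: 54 × 0.44² = 10.5, power 80.9% (stated 80%). This reproduces.
- Aim 2: 54 × 0.45² = 10.9, power 82.8% (stated 80%). The stated figure is slightly conservative.

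So the planned imaging sample is 18 × 3 = 54. The expected sample is somewhat larger: 40 × 0.80 × 0.70 = 22.4 to 40 × 0.85 × 0.70 = 23.8 per arm, or 67 to 71 in all. The false-positive rate hardly depends on this choice.

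**Inputs for the error rate.**

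- BOLD changes for H2b: 5 regions (A2) × 2 imagined tasks (G3) = 10.
- Motor changes: one velocity, or forward and backward velocity (G1).
- Connectivity changes for H3b: not stated. Assumed 5 (one per region) to 10 (all pairs of five regions, 5 × 4 / 2).
- Two-sided 0.05: stated in G1 for Aim 1, assumed here.
- Arms pooled and no true relation: assumed.

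**Critical correlation.** r = t / √(n − 2 + t²). With n = 54 and t = 2.007 on 52 degrees of freedom, r = 2.007 / √(52 + 4.03) = 0.268.

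**Independent tests.** The chance of at least one false positive among m tests is 1 − 0.95^m. If only positive correlations count, it is 1 − 0.975^m.

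- m = 10: 40% and 22%.
- m = 20: 64% and 40%.

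**Correlated measures.** Regions and velocities will be correlated, which lowers these rates. The simulation used n = 54, equal correlation within the imaging set and within the motor set, and no relation between the sets. Separate runs agreed to about 2 percentage points.

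| Imaging × motor changes | Two-sided, correlation 0.5 | Two-sided, correlation 0.8 to 0 | Positive only, correlation 0.5 |
|---|---|---|---|
| 10 × 1 | about 30% | 18–40% | about 15% |
| 10 × 2 | about 47% | 26–65% | about 24% |
| 5 × 1 | about 18% | 13–23% | about 9% |
| 5 × 2 | about 32% | 19–40% | about 16% |

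H2b is the 10-measure rows. H3b lies between the 5-measure and 10-measure rows under the assumed count.

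**With the pairs fixed and FDR applied.** Take the 10 matched H2b tests: five regions with forward imagery against forward velocity, and five with backward imagery against backward velocity. Without adjustment, the two-sided chance of a false positive is 32% at correlation 0.5. With Benjamini-Hochberg FDR at 5%, it is about 4.5%, and about 2.4% counting positive correlations only.

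**Cost in sensitivity.** The smallest correlation detectable with 80% power is tanh[(z₁₋α/₂ + 0.842) / √(n − 3)]. At n = 54 and α = 0.05 this is tanh(2.802 / 7.141) = 0.37. At α = 0.05 / 10 = 0.005, the strictest threshold that FDR applies to 10 tests, it is tanh(3.649 / 7.141) = 0.47.

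**The case against.** The plan has more structure than its closing sentence shows. The regions are specified in advance, the two imagined tasks are separate contrasts, and gait velocity is the declared primary variable of Aim 1. C2 places Aims 2 and 3 under secondary aims, and B2 speaks of exploring potential mechanisms. G3 does state an FDR correction. The hypotheses are directional, so a negative correlation would contradict them and should not be scored as a false confirmation.

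Much of this stands, and it limits the claim.

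- A reader might infer that a false finding is more likely than not. On the H2b grid of 10 BOLD changes and two velocities, the two-sided rate at correlation 0.5 is just under one half, and the positive-only rate is about a quarter.
- A reader might merge H2b and H3b and add non-gait outcomes, reaching 65% (20 imaging changes × 2 velocities) or 90% (20 × 5). The documents do not support those as headline figures. The two hypotheses belong to different aims, the 10 region pairs are an assumption, and A2 speaks of locomotor performance although G3 writes motor performance.
- A reader might say that the plan has no error control. It has FDR for the Aim 2 activation analysis; what is missing is control stated for these correlations.
- A reader might say that any correlation with p below 0.05 would be taken as confirmation, or that the trial intends to claim that exercise works through these brain changes. The plan states no decision rule for the correlations and makes no such causal claim.

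The objection does not remove the gap. Nothing ties the correlations to gait velocity. Nothing labels them exploratory, and H2b and H3b appear under the heading for primary hypotheses in A2. Even if the FDR sentence is stretched to cover H2b, it does not reach the connectivity correlations of H3b.

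**Conclusion.** The concern holds for the secondary imaging hypotheses. As G3 is written, the chance of at least one false direct relation for H2b is about 30% against one velocity and 47% against two, or about 15% and 24% if only positive correlations count. These figures assume 54 people, arms pooled, a two-sided 0.05 cut-off, no true relation and within-set correlation 0.5. For H3b the excess over 5% is similar if 5 to 10 connectivity measures are used, but that count is an assumption.

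The size of the grid is inferred from the document's lists. Separate analyses by arm or by medication state would enlarge it. The primary gait-velocity analysis is not affected, so this should be put right but does not threaten the main result.

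**What to change.** Replace the closing sentence of G3 with a fixed set of tests.

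- **H2b:** correlate the change in each of the five named regions during imagined forward walking with change in forward velocity, and during imagined backward walking with change in backward velocity (10 tests).
- **H3b:** use a list of connectivity measures fixed before analysis and drawn from the regions named in H3a, against change in gait velocity (forward, and backward if listed).
- **Data:** use OFF-medication motor values, to match the scans, and state whether arms are pooled.
- **Decision rule:** apply FDR at 5% within each hypothesis, and count only positive correlations that survive as support.
- **Everything else:** label all other imaging-motor correlations exploratory.

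This changes wording only and needs no new data. The cost is that fewer individual correlations will be called significant: at 54 people, the correlation detectable with 80% power rises from 0.37 to at most 0.47 in a family of 10.

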Parkinson disease (PD) is a progressive, neurodegenerative disorder that affects 1-1.5 million people in the United States. Difficulty with walking has been recognized as one of the earliest signs marking onset of disability in people with PD [1]. Walking difficulties and other symptoms are not fully addressed by current treatment approaches [2, 3], making clear the need for additional approaches. Exercise is one such approach. Current literature supports use of exercise as an adjunct to traditional treatments for improving gait, balance, and quality of life [4]. The primary aims of the proposed work are to compare the effects of three community based exercise programs on locomotor function and to determine whether and how these interventions alter the function and connectivity of locomotor control networks in the brain. To this end, we will utilize task-based functional magnetic resonance imaging (fMRI) and resting state functional connectivity (rs-fc) MRI to assess brain function and connectivity before and after the exercise interventions.

One hundred twenty people with PD will be randomly assigned one of three community-based exercise groups: tango dancing, treadmill training or stretching (control). Tango has been chosen because evidence suggests tango may be superior to a more traditional exercise program for improving gait, balance and quality of life [5, 6]. Treadmill training has been chosen because studies suggest that it can improve gait and quality of life [7]. Stretching has been chosen for the control group because it is an intervention that does not directly target walking and will allow us to control for the social and attentional aspects of participating in group exercise. Each group will receive 3 months of intervention, attending tri-weekly one-hour group classes. Each participant will be evaluated at three time points over 6 months. MRI and behavioral measures will be conducted with participants OFF medication, with behavioral measures also assessed ON medication.

A2 Primary Hypothesis

Hypothesis 1a: Both tango and treadmill training will improve forward walking performance, but only tango will improve backward walking performance. Walking performance in the stretching group will not change.

Hypothesis 1b: Tango and treadmill training will similarly improve disease severity. Tango will result in larger improvements in balance and quality of life compared to treadmill training and stretching.

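### The correlations that test Hypotheses 2b and 3b have no specified adjustment for arm, so arm mean differences can create or mask a brain–walking association

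*Combined protocol and SAP*

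**What the plan says.** Section A2 states two brain–behaviour hypotheses. Hypothesis 2b is that "BOLD signal changes will be directly related to changes in actual locomotor performance". Hypothesis 3b is that "Changes in resting state functional connectivity of the locomotor control network will be directly related to changes in actual locomotor performance".

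Their only stated test is the last sentence of G3: "we will correlate BOLD signal changes during the imagined walking tasks (Aim 2) and changes in connectivity (Aim 3) with changes in motor performance". It names no coefficient, motor variable, arm term or other covariate, and does not say whether the arms are combined or analysed separately. Nothing elsewhere in the document fills the gap.

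Elsewhere in G3, group is named where it is used. The Aim 1 analyses have group and time as factors, Aim 2 compares the three groups by ANCOVA, and the Aim 3 connectivity strengths "will be compared via two-tailed RM ANOVAs with group and time as factors".

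A2 also predicts that the arms will differ on both axes of the correlation:

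- Walking (1a): "Both tango and treadmill training will improve forward walking performance, but only tango will improve backward walking performance", and "Walking performance in the stretching group will not change".
- BOLD (2a): "Following tango, a differential BOLD signal increase will be observed in the premotor area, supplementary motor area, and putamen", during both imagined tasks. Treadmill training is expected to raise other regions (primary somatosensory cortex and cerebellum), during imagined forward walking only. For the controls, "No BOLD signal changes will occur in the stretching group".
- Connectivity (3a): the same split of regions between tango and treadmill, with no change in stretching.

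**The concern.** When arm means differ on both variables, a correlation across the combined arms has two sources: the relation between individuals within an arm, and the alignment of the arm means. The second can be non-zero when the first is zero. If tango raises putamen activity and also improves backward walking, the tango participants sit up and to the right of the others, and a correlation appears even if the tango participants whose putamen changed most walked no better than the rest.

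The difficulty arises when Hypotheses 1a and 2a (or 3a) are true, so success on those hypotheses distorts the test of 2b or 3b. At stake is the only individual-level link between brain and walking in the plan. Without arm in the model, the result cannot separate two changes that occurred in the same arm from a relation in which people whose brain changed more also walked better.

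**Working it through.** **1. Effect-size scale.** G1 gives no sample size or power for these correlations, so I take the effect sizes from the powered aims. For a three-group F test, λ = f²N.

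- Aim 1: f = 0.40, N = 3 × 27 = 81, λ = 0.16 × 81 = 12.96. Power is 89.5% (plan: 89%), which reproduces. Reading 0.4 as Cohen's d gives 31%, so it is f.
- Aim 3: f = 0.44, N = 3 × 18 = 54, λ = 0.1936 × 54 = 10.45. Power is 80.9% (plan: 80%), which reproduces.
- Aim 2: f = 0.45, N = 54, λ = 0.2025 × 54 = 10.94. Power is 82.8% (plan: 80%). This is slightly off, on the safe side; reading 0.45 as d gives 27%.

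**2. Usable scans per arm.** G1 recruits 40 per arm and expects 15–20% attrition and about 30% scan loss: 40 × 0.80 × 0.70 = 22.4 and 40 × 0.85 × 0.70 = 23.8. G1 needs 18. I use 18, 22 and 24.

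**3. Correlation induced by arm means alone.** Take equal arms, within-arm SD of change 1, and zero within-arm correlation. Let c be the correlation between the two patterns of arm means. Then

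r = c·f₁·f₂ / √[(1 + f₁²)(1 + f₂²)].

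With f₁ = 0.45 and f₂ = 0.40, r = c × 0.18 / √(1.2025 × 1.16) = c × 0.18 / 1.181 = 0.152c. Using the Aim 3 value of 0.44 instead, r = c × 0.176 / √(1.1936 × 1.16) = 0.150c, so connectivity behaves in the same way.

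Patterns in the order tango, treadmill, stretching:

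- Tango-only region (1,0,0) with backward walking (1,0,0): c = 1.
- Tango-only region (1,0,0) with forward walking (1,1,0): covariance 1/3 − (1/3)(2/3) = 1/9, each variance 2/9, so c = 0.5.
- Treadmill-only region (0,1,0) with backward walking (1,0,0): covariance 0 − 1/9, so c = −0.5. This pair uses connectivity, or BOLD during imagined forward walking.

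**4. Rejection rates.** Simulation with 20,000 trials per scenario, two-sided 0.05, true within-arm correlation zero:

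| Pair | Induced r | 18/arm | 22/arm | 24/arm |
|---|---|---|---|---|
| Tango-only region × backward | 0.15 | 20% | 23% | 25% |
| Tango-only region × forward | 0.08 | 8% | 9% | 10% |
| Treadmill-only region × backward | −0.08 | 8% | not run | not run |

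In the third row almost all rejections are negative; only 0.6% of trials are significantly positive. With changes centred within arm (partial correlation, N − 4 degrees of freedom), the rate is 4.7–5.3% across all scenarios run.

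**5. Sensitivity to the SD of change.** The document gives only a cross-sectional gait SD of 0.1 m/s. A tango-only shift at f = 0.40 equals 0.40/0.471 = 0.849 SD of change, where 0.471 = √(2/9). For a shift of 0.1 m/s, that implies a change SD of 0.1/0.849 = 0.118 m/s. If instead the change SD is 0.1 × √[2(1 − ρ)], with the pre–post correlation ρ assumed, then for a tango-only region × backward walking, BOLD f = 0.45 and 18 per arm:

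| ρ (assumed) | Change SD (m/s) | Induced r | p<0.05 |
|---|---|---|---|
| 0.5 | 0.100 | 0.18 | 25% |
| 0.7 | 0.077 | 0.21 | 35% |
| 0.8 | 0.063 | 0.25 | 44% |
| 0.9 | 0.045 | 0.30 | 62% |

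**6. Precision.** The detectable r at 80% power is tanh[(1.96 + 0.8416)/√(N − 3)]: 0.37 for N = 54, 0.34 for N = 66, 0.33 for N = 72, and 0.62 within one arm of 18.

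**The case against.** **The text is silent, not explicit.** A reader might infer that the plan commits to a pooled, unadjusted correlation. It does not say so. Correlations run separately within each arm would avoid the problem, and Hypothesis 3b adds that stretching will show no changes, which hints at an arm-aware reading. This stands, and it limits the point to what is unspecified. It does not remove the point: group is named elsewhere in G3 but not here, and the detectable r (0.62 within one arm of 18, 0.37 across 54) makes combining the arms the natural choice.

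**The bias need not favour the hypotheses.** A reader might infer that arm differences always produce a spurious direct relation. They do not: sign and size depend on the pair, and a treadmill-only region against backward walking is pushed negative. This stands.

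**Rejection is an error only for one target.** When arm means differ, the combined-arm correlation is truly non-zero. Rejecting zero is false only if the target is the within-arm relation, and 2b and 3b do not define their target. Adjusting for arm sets aside the randomised contrast and keeps observational variation between individuals. This stands, and is a reason to state the target. The arm contrasts already have their own analyses under Aims 2 and 3, so the within-arm relation is what this sentence can add.

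**Importance.** C2 lists Aims 2 and 3 as secondary, and no power is claimed for the correlations. That is fair, although 2b and 3b sit under the primary hypothesis heading in A2. The false discovery rate correction given for Aim 2 addresses multiplicity, not confounding by arm.

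**Conclusion.** The concern holds as a gap in specification with a definite consequence. G3 specifies no arm adjustment for the only test of 2b and 3b, and if its sentence is followed across the combined arms, the result mixes arm differences with the individual-level relation.

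At the planning effect sizes the artefact is modest: an absolute induced r of about 0.08 to 0.15, and p<0.05 in roughly 8–25% of trials instead of 5%. A reader might take the upper end to be about 30%. That needs a tango-only shift of a full SD of change in both variables (r = 0.18; 26% at 18 per arm, 31% at 22), which is more than the plan's f of 0.45 and 0.40 imply.

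The figures assume equal arms, no within-arm relation, effect sizes read as Cohen's f and applied to change scores, and arm patterns exactly as hypothesised. The SD of change is the main unknown; for a fixed shift in m/s, a smaller one makes the artefact larger. The analysis should be changed, but the aims' main group comparisons are not affected.

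**What to change.** In G3, replace the simple correlation with a regression of motor change on BOLD or connectivity change that includes arm as a factor; a partial correlation adjusted for arm is equivalent for the test. Report the common within-arm slope with its confidence interval, and label the arm-by-imaging-change interaction exploratory. State in the same place that the target is the within-arm, individual-level relation.

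The cost is the wording and two degrees of freedom, with no new data. The estimate will not speak to whether arms with larger mean brain changes also had larger mean walking changes; the group comparisons describe that. If a within-arm or adjusted analysis was already intended, one sentence saying so closes the point.
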